Some centers will have few eligible subjects only. Therefore, the centers will be pooled together by country except for

- sites that have more than 12 subjects in the FAS (i.e. these sites will not be pooled with any other site).
- for countries that have 6 subjects or less in the FAS that will be pooled as follows:
- Scandinavia = Finland and Sweden
- Mediterranean = Italy and Spain
- Austria-Hungary = Austria and Hungary

MRI specific covariates

Time between scans: in Months

Time between scans (in Months) is calculated as follows:

- Time between scans (in Months) = (MRI date of the Visit - MRI of the previous Visit + 1) / 30.4375. i.e.:
 - If (Visit=Month 1) then Time between scans (in Months) = (MRI date at Month 1 - MRI date at Baseline + 1) / 30.4375
 - If (Visit=Month 2) then Time between scans (in Months) = (MRI date at Month 2 - MRI date at Month 1 + 1) / 30.4375
 - If (Visit=Month 3) then Time between scans (in Months) = (MRI date at Month 3 - MRI date at Month 2 + 1) / 30.4375
 - If (Visit=Month 6) then Time between scans (in Months) = (MRI date at Month 6 - MRI date at Month 3 + 1) / 30.4375

If the corresponding MRI is available and the time between scans is missing (due to preceding MRI being missing) it will be replaced by expected time as follows:

- Month 1/2/3 Visit =1
- Month 6 Visit =3.

Time between scans: in Years

Time between scans (in Years) is calculated as follows:

- Time between scans (in Years) = (MRI date of the Visit - MRI of the previous Visit + 1) / 365.25, i.e.:
 - If (Visit= Month 1) then Time between scans (in Years) = (MRI date at Month 1 - MRI date at Baseline + 1) / 365.25
 - If (Visit= Month 2) then Time between scans (in Years) = (MRI date at Month 2 - MRI date at Month 1 + 1) / 365.25
 - If (Visit= Month 3) then Time between scans (in Years) = (MRI date at Month 3 - MRI date at Month 2 + 1) / 365.25
 - If (Visit= Month 6) then Time between scans (in Years) = (MRI date at Month 6 - MRI date at Month 3 + 1) / 365.25
 - If (Visit= Month 12) then Time between scans (in Years) = (MRI date at Month 12 - MRI date at Month 6 + 1) / 365.25
 - If (Visit= Month 15) then Time between scans (in Years) = (MRI date at Month 15 - MRI date at Month 12 + 1) / 365.25
 - If (Visit= Month 18) then Time between scans (in Years) = (MRI date at Month 18 - MRI date at Month 15 + 1) / 365.25
 - If (Visit= Month 24) then Time between scans (in Years) = (MRI date at Month 24 - MRI date at Month 18 + 1) / 365.25

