If the corresponding MRI is available and the time between scans is missing (due to preceding MRI being missing) it will be replaced by expected time as follows:

- Month 1/2/3 Visit =1
- Month 6 Visit =3
- Month 12 Visit =6
- Month 15 Visit =3
- Month 18 Visit =3
- Month 24 Visit =6.

Software(s)

All analyses will be performed using SAS® Software version 9.3, or higher.

10 Trial Participants

The subsections in this section include specifications for reporting subject disposition and treatment/study discontinuation. Additionally, procedures for reporting protocol deviations are provided.

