 - and any Lymphocyte count < 800 cells/mm³ at or after Month 12 Visit and before start of Treatment Course 2.
- Before or at / after Start of COVID-19 pandemic

The cumulative dose is defined as the sum of the number of tablets taken 10 mg divided by the weight for treatment year:

Cumulative dose = number of tablets taken in Treatment Course 1 * 10mg / weight in kg at Baseline + number of tablets taken in Treatment Course 2 * 10mg / weight in kg at Month 12b Visit.

The cumulative dose will be calculated only if the weight and number of tablets are available. Otherwise it will be missing. If the Treatment Course 2 wasn't started (i.e. no tablet taken in Treatment Course 2), the cumulative dose will be calculated only for the Treatment Course 1.

A subject data listing of the treatment compliance will be provided for the SAF.

14 Efficacy Analyses

The following sections describe the planned analyses for each of efficacy endpoints.

For the detailed definition of covariates and stratification factors that are used in the statistical models see Section 9. Details about the derived MRI endpoints and general handling of MRI data is described in Section 9 (“Data Handling of MRI data”).

Descriptive summary statistics will be presented for the absolute values and the changes from Baseline as applicable by Visit [Protocol Scheduled Visits except for Baseline (defined in Section 9)], or Period, for all efficacy endpoints (and the components, where applicable) for the FAS and respective subgroups or subsets for which the variables are analyzed. Details about the presentation of continuous and categorical variables are given in Section 9.

Wherever possible, all estimated results from the statistical models will be calculated with the same observed margin which reflects the population of the whole corresponding analysis set, regardless of missing data.

14.1 Primary Endpoints: Differences in the counts of CUA MRI lesions during the first 6 months compared to Baseline

The primary endpoints for the trial are defined as the differences in counts of CUA MRI lesions during the first 6 months compared to Baseline, i.e., the following differences will be evaluated:

1. Period of Month 1 to Month 6 compared to the Baseline Period.
2. Period of Month 2 to Month 6 compared to the Baseline Period.
3. Period of Month 3 to Month 6 compared to the Baseline Period.

For the detailed definition of Periods, please see Section 9 “Data Handling of MRI data”.

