Tertiary (FAS)	Period 24.1 (Baseline-Month 24): #CUA(p24.1)/#CUA(p0)	Generalized model assuming a negative binomial distribution with the following adjusting factors: 
 • Age (years), • EDSS at Baseline (≤3, >3), Estimated standardized CUA for the Periods as well as the ratios of the post-Baseline Period versus the Baseline Period, and corresponding Standard Errors (SE) will be presented including estimated fixed effects including the SE, 2-sided p-values and 95% CI.	Same as above for the generalized model.
Tertiary (FAS by subgroup "High-relapse activity")			
Tertiary (FAS by subgroup "Previous treatment with DMDs")			
Tertiary endpoints: Change from the Baseline Period in Annualized CUA lesion count to the yearly post-Baseline Periods excluding the first month			
Tertiary (FAS)	Period 11.1 (Month 1-12): ΔCUA(p11.1)	Mixed-effects linear model as specified above.	Same as in the Primary Analysis (see Section 14.1.1).
Tertiary (FAS by subgroup "High-relapse activity")	Period 11.2 (Month 1-24): ΔCUA(p11.2)		
Tertiary (FAS by subgroup "Previous treatment with DMDs")			

Analysis (Analysis Set)	Derivation	Statistical Analysis Methods	Missing data handling
Tertiary endpoints: Ratio of the yearly post-Baseline Periods excluding the first month versus the Baseline Period in Annualized CUA lesion count			
Tertiary (FAS)	Period 11.1 (Month 1-12): $\Delta\text{CUA}(p11.1)$	Generalized model as specified above.	Same as above for the generalized model.
Tertiary (FAS by subgroup "High-relapse activity")	Period 11.2 (Month 1-24): $\Delta\text{CUA}(p11.2)$		
Tertiary (FAS by subgroup "Previous treatment with DMDs")			
Tertiary endpoint: Change from Baseline in Annualized CUA lesion count by Visit			
Tertiary (FAS)	Change from Baseline in CUA lesion count at Month i Visit, where i= 1, 2, 3, 6, 12, 15, 18 and 24.	Mixed-effects linear model for repeated measures with the following adjusting factors: 
 • Baseline score, • Age (years), • EDSS at Baseline (≤ 3, > 3), • Visit⁵, • Time between scans (years), • Pooled center, • Within-subject correlation. Estimated Least Square Means (LS Means) and corresponding Standard Errors (SE) will be presented by Visit including 2-sided p-values and 95% CI.	Same as above for mixed effect linear model with repeated measures.
Tertiary (FAS by subgroup "High-relapse activity")			
Tertiary (FAS by subgroup "Previous treatment with DMDs")			

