Tertiary Endpoint: CUA lesion count > 0			
Tertiary (FAS)	Cross-tabulation for each post-Baseline Period: 
 • No: $\#\text{CUA}(p_{\text{post-Baseline}}) = 0$ • Yes: $\#\text{CUA}(p_{\text{post-Baseline}}) > 0$ vs Baseline Period: 
 • No: $\#\text{CUA}(p_0) = 0$ • Yes: $\#\text{CUA}(p_0) > 0$ 	McNemar Test.	Missing observations at Baseline: Subjects with a missing Baseline score will not be included in McNemar Test, however separate cross-tabulation table including missing/not-evaluable lesions counts will be presented and thus providing percentage related to all subjects. Missing post-Baseline observations: Same as above but adapted for missing post-Baseline observations (see "Missing observations at Baseline").
Tertiary (FAS by subgroup High-relapse activity)			
Tertiary (FAS by subgroup "Previous treatment with DMDs")			
ΔCUA = Difference in the annualized CUA lesion count between post-Baseline Periods and the Baseline Period $\#\text{CUA}$ = Annualized CUA lesion count during Periods			

Analysis (Analysis Set)	Derivation	Statistical Analysis Methods	Missing data handling
p ₀ = Baseline Period \$=Sequential Visit Periods			

Mixed-effects linear model for repeated measures

The change from Baseline in the annualized CUA lesion count by Period or Visit (i.e. the Sequential Visit Period) will be analyzed by a repeated mixed-effects linear model, which adjusts for the Baseline score (i.e. the annualized count), age (in years), EDSS at Baseline (≤ 3 , > 3), pooled center, Period /or Visit, within subject correlation and time between scans (in years), where applicable. An unstructured covariance matrix will be assumed for the model. If the model doesn't converge an alternative covariance structure will be used instead.

The estimated annualized CUA lesion count will be calculated based on the observed margin of the corresponding analysis set at Baseline.

Mixed-effects linear model

The change from Baseline in annualized CUA lesion count for each Period separately will be analyzed by a mixed-effects linear model, which adjusts for the Baseline score (i.e., the annualized count), age (in years), EDSS at Baseline (≤ 3 , > 3), pooled center, time between scans (in years) and within subject correlation. An unstructured covariance matrix will be assumed for the model. If the model doesn't converge an alternative covariance structure will be used instead.

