Tertiary (FAS)	Period 12.1 (Baseline-Month 12): $\#T1(p_{12.1})/\#T1(p_0)$	Generalized model as specified as above.	Same as above for the generalized model.
Tertiary (FAS by subgroup "High-relapse activity")	Period 12.2 (Month 12-24): $\#T1(p_{12.2})/\#T1(p_0)$		
Tertiary (FAS by subgroup "Previous treatment with DMDs")			

Analysis (Analysis Set)	Derivation	Statistical Analysis Methods	Missing data handling
Tertiary endpoint: Change from the Baseline Period in T1 Gd+ lesion count to the 2-year post-Baseline Period			
Tertiary (FAS)	Period 24.1 (Baseline-Month 24): $\Delta T1(p_{24.1})$	Mixed-effects linear model same as in Tertiary Analysis for Change from Baseline in CUA lesion count (see Section 14.3.1)	Same as in Tertiary Analysis for Change from Baseline in CUA lesion count (see Section 14.3.1)
Tertiary (FAS by subgroup "High-relapse activity")			
Tertiary (FAS by subgroup "Previous treatment with DMDs")			
Tertiary endpoints: Ratio of the 2-year post-Baseline Period versus the Baseline Period in T1 Gd+ lesion count			
Tertiary (FAS)	Period 24.1 (Baseline-Month 24): $\#T1(p_{24.1}) / \#T1(p_0)$	Generalized model assuming a negative binomial distribution with the following adjusting factors: 
 • Age (years), • EDSS at Baseline ($\leq 3, >3$), Estimated T1 Gd+ lesions count for the Periods as well as the ratios of the post-Baseline Period versus the Baseline Period, and corresponding Standard Errors (SE) will be presented including estimated fixed effects including the SE, 2-sided p-values and 95% CI.	Same as above for the generalized model.
Tertiary (FAS by subgroup "High-relapse activity")			
Tertiary (FAS by subgroup "Previous treatment with DMDs")			
Tertiary endpoint: Change from Baseline in T1 Gd+ lesion count by Visit			
Tertiary (FAS)	Change from Baseline in T1 Gd+ lesion count at Month i Visit, where $i = 1, 2, 3, 6, 12, 15, 18$ and 24.	Mixed-effects linear model for repeated measures, same as in Tertiary Analysis for Change from Baseline in CUA lesion count (see Section 14.3.1)	Same as in Tertiary Analysis for Change from Baseline in CUA lesion count (see Section 14.3.1)
Tertiary (FAS by subgroup "High-relapse activity")			
Tertiary (FAS by subgroup "Previous treatment with DMDs")			
Tertiary Endpoint: T1 Gd+ lesion count > 0			

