Tertiary (FAS)	Annualized PBVC at Month i Visit, where i=1, 2, 3, 6, 12 and 24.	Mixed-effects linear model for repeated measures for the change from Baseline with the following adjusting factors: 
 • Baseline value, • Age (in years), • EDSS at Baseline (≤ 3, > 3), • Visit, • Time between scans (years), • Within-subject correlation. Estimated Least Square Means (LS Means) and corresponding Standard Errors (SE) will be presented by Visit including 2-sided p-values and 95% CI.	Missing observations at Baseline: Subjects with a missing Baseline brain volume will not be included in the linear model. Missing post-Baseline observations: Missing post-Baseline assessments will not be imputed. The repeated measurement model handles missing post-Baseline assessments under the assumption of MAR.
	Annualized PBVC 
 • $\leq -0.4\%$ • $> -0.4\%$ during the Treatment Period.	Descriptive summary statistics.	
Tertiary endpoints: Annualized percentage white matter brain volume change from Baseline			
Tertiary (FAS)	Annualized PWMBVC at Month 24 Visit.	Descriptive summary statistics.	
	Annualized PWBVC 
 • $\leq -0.4\%$ • $> -0.4\%$ at Month 24 Visit.		

Tertiary endpoints: Annualized percentage grey matter brain volume change from Baseline			
Tertiary (FAS)	Annualized PGMBVC at Month 24 Visit.	Descriptive summary statistics.	
	Annualized PGMBVC 
 • ≤ -0.4% • > -0.4% at Month 24 Visit.		
Tertiary endpoints: Annualized percentage deep grey matter brain volume change from Baseline			
Tertiary (FAS)	Annualized PDGMBVC change at Month 24 Visit.	Descriptive summary statistics.	
	Annualized PDGMBVC 
 • ≤ -0.4% • > -0.4% at Month 24 Visit.		
Tertiary endpoints: Percentage brain volume change from Baseline			
Tertiary (FAS)	PBVC change at Month 24 Visit.	Descriptive summary statistics.	
Tertiary endpoints: Percentage white matter brain volume change from Baseline			
Tertiary (FAS)	PWMBVC change at Month 24 Visit.	Descriptive summary statistics.	
Tertiary endpoints: Percentage grey matter brain volume change from Baseline			
Tertiary (FAS)	PGMBVC change at Month 24 Visit.	Descriptive summary statistics.	
Tertiary endpoints: Percentage deep grey matter brain volume change from Baseline			
Tertiary (FAS)	PDGMBVC change at Month 24 Visit.	Descriptive summary statistics.	

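### Tertiary by-Visit models include both Visit and time since the previous scan, which the schedule almost fixes. With one common margin, LS means at Months 1-3, 12 and 24 become imprecise and refer to an unplanned gap.

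*SAP*

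**What the plan says.** SAP Section 14.3.1 specifies the by-Visit CUA model with Visit and "Time between scans (years") as separate adjusting factors. Its model text repeats this: "Period /or Visit, within subject correlation and time between scans (in years), where applicable". Section 14.3.2 lists the same two terms for the absolute CUA count. Section 14.3.3 applies the 14.3.1 model to "Change from Baseline in T1 Gd+ lesion count at Month i Visit", and Section 14.3.7 applies it to annualized active T2 by Visit. Section 14.3.11 lists both terms for "Annualized PBVC at Month i Visit".

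Section 9 defines the covariate: "Time between scans (in Years) = (MRI date of the Visit - MRI of the previous Visit + 1) / 365.25". It also gives the expected gaps used when the preceding scan is missing, for example "Month 1/2/3 Visit =1" and "Month 12 Visit =6". Months 6, 15 and 18 are given 3, and Month 24 is given 6.

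On the margin, the opening of Section 14 says that, as far as can be done, "all estimated results from the statistical models will be calculated with the same observed margin which reflects the population of the whole corresponding analysis set". Section 14.3.1 refers to the observed margin at Baseline, but Section 9 defines no gap before Month 1. Neither section states the value at which the gap is held, and neither centres it within visit. Results are reported as LS means by Visit with SE, p-value and 95% CI.

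**The concern.** A covariate that is nearly a function of Visit carries almost no information beyond Visit. Its slope is poorly determined. An LS mean taken at a gap far from that visit's own gap is the visit mean plus that slope times the distance, so it inherits the slope's imprecision.

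The purpose of the term is also unclear. T1 Gd+ is read on a single scan. The T2 part of CUA and active T2 are already annualized over their own period. PBVC is annualized over the interval from Baseline, whereas the covariate measures the gap since the previous visit. At Month 24 that gap runs from the Month 18 scan, which the PBVC model does not use.

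At stake are the adjusted visit-by-visit estimates, with their CIs and p-values. These include the early visits, which are of most interest for onset of action.

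**Working it through.** The documents give no figure on this point, so the check starts from the schedule. It concerns the 24-month models.

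**1. Scheduled gaps** (SAP Section 9): 1+1+1+3+6+3+3+6 = 24 months, with running totals 1, 2, 3, 6, 12, 15, 18 and 24, matching the visits. The mean is 24/8 = 3.0 months. For the six PBVC visits it is also (1+1+1+3+6+6)/6 = 3.0.

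**2. Gaps possible inside the windows.** For a scheduled gap of m months (30 days each) and scatter of ±w days at both scans, the range in months is (30m ± 2w + 1)/30.4375. Protocol Section 7 gives w = 7, and w = 12 if the further ±5 days for the MRI is added.

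| Scheduled gap | Visits | w = 7 | w = 12 |
|---|---|---|---|
| 1 month | 1, 2, 3 | 17/30.4375 to 45/30.4375 = 0.56-1.48 | 0.23-1.81 |
| 3 months | 6, 15, 18 | 2.53-3.45 | 2.20-3.78 |
| 6 months | 12, 24 | 5.49-6.41 | 5.16-6.74 |

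The three ranges do not overlap, so any single value lies outside the planned range at 5 or more of the 8 visits. At 3.0 months these are Months 1, 2, 3, 12 and 24.

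**3. Collinearity** (simulated uniform scatter). Visit explains 99.1% of the gap's variance at ±7 days (variance inflation factor about 112) and 97.4% at ±12 days (about 39).

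**4. Formula.** With common gap t* and visit mean gap t_v, the LS mean is the visit mean + slope × (t* − t_v). Its variance is approximately SE0² + (t* − t_v)² × SE_slope², where SE0 is the standard error without the covariate. In days, the mean gaps are 31, 91 and 181 and t* is 91. The distances are therefore 60/365.25 = 0.164 year at Months 1-3, zero at Months 6, 15 and 18, and 90/365.25 = 0.246 year in the other direction at Months 12 and 24.

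**5. Numbers.** Assumptions: N = 250, subject SD 1.0, residual SD 1.1, compound symmetry, complete data. Total SD = √(1.00 + 1.21) = 1.487, so SE0 = 1.487/√250 = 0.094. The simulated SE of the slope is about 1.64 per year at ±7 days and 0.95 at ±12 days.

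| | ±7 days | ±12 days |
|---|---|---|
| Months 1-3 | √(0.094² + (0.164×1.64)²) = 0.28, ×3.0 | 0.18, ×1.9 |
| Months 6, 15, 18 | 0.094, ×1.0 | 0.094, ×1.0 |
| Months 12, 24 | √(0.094² + (0.246×1.64)²) = 0.41, ×4.4 | 0.25, ×2.7 |

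Months 1, 2 and 3 share one scheduled gap and move together. The SE of Month 2 minus Month 1 is √(2×1.21/250) = 0.098 with or without the covariate.

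**6. Sensitivity.** With N = 265, SD 1 and within-subject correlation 0.3, the factors at Months 1-3 and at Months 12/24 are 3.4 and 5.0 at ±7 days, 2.1 and 3.0 at ±12 days, and 7.6 and 11.3 at ±3 days.

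**7. After the fix.** If the term is dropped, or centred so that each visit is evaluated at its own gap, then t* − t_v = 0 throughout. The shift is 0 and the SE factor is about 1.0.

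**The case against.** The best counter-case has five parts.

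- **The common value is not written down.** The margin rule is qualified and speaks of the population, and the Baseline margin has no meaning for this covariate. This stands: 3 months is an inference. The non-overlap in step 2, however, applies to any single value.
- **The analyses are minor.** They are tertiary and exploratory (protocol Section 8.5.1). A reader might infer that they alone show when activity falls. The documents do not support that: the ordered primary tests on Months 3-6, 2-6 and 1-6 do not use this covariate, and Section 14 plans descriptive summaries by Visit or Period for all efficacy endpoints. This stands in full and lowers the severity.
- **Not the whole curve is affected.** A reader might infer that every visit is extrapolated to gaps that never occur. That is too strong. Months 6, 15 and 18 sit at their own gap, early contrasts are preserved, and Section 9 keeps out-of-window scans, so atypical gaps can arise.
- **The inflation depends on scatter.** If 5% of scans from Month 6 onward were 30-90 days late for unrelated reasons (assumed), the Months 1-3 factor falls to about 1.4. Section 9 also fills missing gaps in the years variable with month numbers. Taken literally with 2% filled, those values dominate the slope and the inflation disappears (×1.0), but only because the term then mostly flags a missing earlier scan. With the units corrected the factors return to about 3.1 and 4.5.
- **Bias has no established direction.** A reader might infer from postponed scans after relapse that early means are pushed up and late means down. If 3% of scans are 14-28 days late with one extra lesion, the shifts are about +0.7 at Months 1-3 and −0.9 to −1.0 at Months 12 and 24. But protocol Section 7.3.1.1 also brings scans forward. If instead 3% of Month 6 scans come 14-56 days early with one extra lesion, the signs reverse, to about −0.1 to −0.2 and +0.2 to +0.3.

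**Conclusion.** The point holds for the tertiary by-Visit models in SAP Sections 14.3.1, 14.3.2, 14.3.3, 14.3.7 and 14.3.11. Time between scans nearly duplicates Visit. Under one shared margin, the LS means at 5 of 8 visits refer to a gap outside the planned range, with standard errors about 3.0 times (Months 1-3) and 4.4 times (Months 12 and 24) the unadjusted ones at ±7 days, or 1.9 and 2.7 times at ±12 days.

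These sizes rest on an inferred common value of about 3 months, assumed SDs, N = 250, uniform scatter, and fill-in values in consistent units. With no relation between gap and lesions, the LS means are unbiased but imprecise. If gap length is related to relapse they can also be biased, in a direction the documents do not settle. No confirmatory result depends on this. It is a worthwhile, low-cost improvement rather than an essential correction.

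**What to change.** Remove time between scans from the by-Visit models of T1 Gd+ and annualized PBVC. For annualized CUA and annualized active T2, either remove it or replace it by actual minus scheduled gap, centred within visit. State that each LS mean is evaluated at that visit's own scheduled gap. If the term is kept anywhere, express the fill-in values of the years variable in years, and say how the Baseline record in Section 14.3.2 is handled, since it has no defined gap.

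The cost is a few lines of SAP text and one line of model code. No new data are needed.

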14.3.2 CUA lesion count

CUA lesion counts for the Sequential Visit Periods are defined in the Section 9 "Definition of Study Periods" and "Data Handling of MRI data".

Analysis (Analysis Set)	Derivation	Statistical Analysis Methods	Missing data handling
Tertiary endpoint: Annualized CUA lesion count by Visit			
Tertiary (FAS)	Absolute CUA lesion count at Month i Visit, where i= 0, 1, 2, 3, 6, 12, 15, 18 and 24.	Mixed-effects linear model for repeated measures for the absolute values over 24 months with the following adjusting factors: 
 • Baseline score, • Age (in years), • EDSS at Baseline (≤ 3, > 3), • Visit[§], • Time between scans (years), • Pooled center, • Within-subject correlation. Estimated Least Square Means (LS Means) and corresponding Standard Errors (SE) will be presented by Visit including 95% CI.	Same as for mixed effect linear model with repeated measures in Section 14.3.1
Tertiary (FAS by subgroup "High-relapse activity")			
Tertiary (FAS by subgroup "Previous treatment with DMDs")			
§=Sequential Visit Periods			

Mixed-effects linear model for repeated measures

As defined in Section 14.3.1 applying adaptations to the endpoints, factors and covariates listed in the table above.

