The last non-missing measurement prior to start of study medication will serve as the Baseline measurement. Measurements performed on the day of first intake of study medication are assumed to be “prior to start of study medication”, as long as it has not been confirmed that the procedure was performed afterwards. This assumption is justified as following the sequence of procedures as specified in the study protocol. The intake of study medication should be the last procedure on the Visit day.

The MRI scans will be reconciled during central MRI review process. Therefore, MRIs will be considered as Baseline MRIs if assigned to the Baseline Visit by the central imaging review.

Definition of Study Periods

- Baseline Period: The Baseline Period is defined as the Period between the Screening and the Baseline MRI scan.
- Post-Baseline Period: The post-Baseline Periods that are used in the primary analysis are defined as follows:
 - Period 1 (p₁) is defined as the Period between Month 1 and Month 6 MRI scans.
 - Period 2 (p₂) is defined as the Period between Month 2 and Month 6 MRI scans
 - Period 3 (p₃) is defined as the Period between Month 3 and Month 6 MRI scans

In addition, the following post-Baseline Periods are defined solely for tertiary analyses:

Three months Periods

- Period 3.1 (p_{3.1}) is defined as the Period between Baseline and Month 3 MRI scans.

Six months Periods

- Period 6.1 (p_{6.1}) is defined as the Period between Baseline and Month 6 MRI scans,
- Period 6.2 (p_{6.2}) is defined as the Period between Month 6 to Month 12 MRI scans,
- Period 6.3 (p_{6.3}) is defined as the Period between Month 12 to Month 18 MRI scans,
- Period 6.4 (p_{6.4}) is defined as the Period between Month 18 to Month 24 MRI scans.

Periods excluding the Period between the Baseline scan and the Month 1 MRI scan:

- Period 11.1 (p_{11.1}) is defined as the Period between Month 1 to Month 12 MRI scans,
- Period 11.2 (p_{11.2}) is defined as the Period between Month 1 to Month 24 MRI scans.

Yearly Periods:

- Period 12.1 (p_{12.1}) is defined as the Period between Baseline to Month 12 MRI scans,
- Period 12.2 (p_{12.2}) is defined as the Period between Month 12 to Month 24 MRI scans.

2 -Year Period:

- Period 24.1 (p_{24.1}) is defined as the Period between Baseline to Month 24 MRI scans.

Sequential Visit Periods

- Period 100.0 (p_{100.0}) is defined as the Period between Screening and Baseline (equivalent to Baseline Period) MRI scans

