The estimated annualized CUA lesion count will be calculated based on the observed margin of the corresponding analysis set at Baseline.

Generalized linear model assuming negative binomial distribution

The annualized CUA lesion count will be evaluated using a generalized mixed-effects linear model with log link function assuming a negative binomial distribution. Period (i.e. Baseline Period, each post-Baseline Period as specified above) will be analyzed as: a) a repeated factor accounting for time between scans (in years) if the time is different between scans, or b) neglected, if the time between scans is constant (for example: for every 6 months Periods, 1 yearly Periods); and within subject correlation using an unstructured covariance matrix. Age and EDSS at Baseline (≤ 3 , > 3) will be used as fixed effect covariates.

The ratio of the annualized CUA lesion count of each post-Baseline Period versus the Baseline Period will be calculated as the inverse log of the difference of the estimated contrast between each post-Baseline Period and the Baseline Period.

Offset will be applied if needed.

The estimates, standard deviation and 95% confidence intervals for the annualized CUA lesion count at each Period and the ratio between Periods will be presented together with the estimated fixed effects. If the model doesn't converge an alternative covariance structure will be used instead of the unstructured covariance matrix.

The estimated annualized CUA lesion count will be calculated based on the observed margin of the corresponding analysis set at Baseline.

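### SAP 14.3.2: the tertiary absolute-CUA model uses the Baseline value as both Month 0 response and covariate, so it has no valid fit under the specified unstructured covariance

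*SAP*

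**What the plan says.** SAP 14.3.2 specifies a "Mixed-effects linear model for repeated measures for the absolute values over 24 months with the following adjusting factors", and the first factor listed is the Baseline score. The response is "Absolute CUA lesion count at Month i Visit, where i= 0, 1, 2, 3, 6, 12, 15, 18 and 24".

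Four other statements in the SAP fix what this means:

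- A footnote to the 14.3.2 table equates Visit with the Sequential Visit Periods. Section 9 (Definition of Study Periods) says that Period 100.0 "is defined as the Period between Screening and Baseline (equivalent to Baseline Period) MRI scans".
- Section 14.3.1 describes the repeated-measures model as one "which adjusts for the Baseline score (i.e. the annualized count").
- Section 14.3.2 takes over that model: "As defined in Section 14.3.1 applying adaptations to the endpoints, factors and covariates listed in the table above".
- Section 14.3.1 states "An unstructured covariance matrix will be assumed for the model". If the model does not "converge an alternative covariance structure will be used instead". The alternative is not named.

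The missing-data rule of 14.3.1, which also applies here, leaves out subjects without a Baseline score. The table promises LS means, standard errors and 95% confidence intervals by Visit, with no p-values.

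**The concern.** At Month 0 the model regresses the Baseline count on itself. A covariate that reproduces one of the responses exactly leaves no residual variation at that visit once its slope equals 1. An unstructured covariance gives that visit its own variance, so nothing stops the variance from going to zero.

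The 14.3.2 model is the only one listed for the level of CUA by Visit over 24 months, and it is repeated in the high-relapse-activity and previous-DMD subgroups. If the specified model fails, the reported one will use a covariance structure chosen afterwards, with a Baseline slope that the Month 0 rows have distorted.

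**Working it through.** The documents give no numerical result for this analysis, so there is no figure to reproduce.

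**Inputs.** Nine response visits, Month 0 included (SAP 14.3.2). One common Baseline slope, since no Baseline-by-Visit term is listed. Unstructured covariance (14.3.1). N = 265, the planned number (protocol synopsis).

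**Step 1: identity.** Period 100.0 equals the Baseline Period, and the Baseline score is the annualized count of that period. Hence Y_i0 = B_i. Subjects with missing B_i are excluded, so this holds for everyone in the model.

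**Step 2: likelihood.** Write β for the common slope and set the other covariate coefficients to zero. After fitting the Month 0 mean, the Month 0 residual is (1 − β)(B_i − B̄), so the fitted Month 0 variance is (1 − β)² times the variance of B. Given that residual, the fit at the later visits does not depend on β, because the free covariances absorb it. Therefore

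logL(β) = constant − N·ln|1 − β|.

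Each tenfold cut in 1 − β adds 265 × ln 10 = 610.2. In a simulated dataset with N = 265 and nine visits:

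| β | logL |
|---|---|
| 0 | −6092.9 |
| 0.9 | −5482.7 |
| 0.99 | −4872.5 |
| 0.999 | −4262.4 |
| 0.99999 | −3042.0 |

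The first step checks: −6092.9 + 610.2 = −5482.7. Over this range the Month 0 variance falls from 153 to 153 × (10⁻⁵)² ≈ 1.5 × 10⁻⁸. There is no interior maximum.

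**Step 3: other covariates and REML.** These do not remove the problem, since their coefficients can be zero. A simulated dataset with N = 250 had age, EDSS, time between scans and 15 pooled centers as fixed effects. Once the Month 0 variance is small, each further 100-fold fall raises the ML criterion by about 575 (250/2 × ln 100 = 575.6) and the REML criterion by about 532. The slope goes to 1.0000.

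**Step 4: fallback.** Any structure with a separate Month 0 variance has the same singularity. Homogeneous structures such as compound symmetry or AR(1) do not. For compound symmetry, 300 trials per scenario were simulated. Assumed inputs: Month 0 mean 8, later means falling from 7.2 to 0.8, overdispersed counts, no time covariate. LS means were taken at observed margins, because "The estimated annualized CUA lesion count will be calculated based on the observed margin of the corresponding analysis set at Baseline". The table compares fits with and without Month 0 in the response; the bias is at Month 24, where the true mean is 0.80.

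| Missingness (at Month 24) | Slope with / without | Bias with / without |
|---|---|---|
| None | 0.256 / 0.163 | 0 / 0 |
| Completely random, 21.5% | 0.285 / 0.180 | +0.03 / +0.03 |
| Baseline-dependent, 20% | 0.462 / 0.258 | +1.22 / +0.65 |
| Baseline-dependent, 31% | 0.697 / 0.327 | +2.85 / +1.33 |

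With complete data the LS means equal the raw visit means (largest difference 1.5 × 10⁻¹³). The model standard error is then 0.409 at every visit with Month 0 and 0.355 without, while the empirical SD runs from 0.88 at Month 0 to 0.11 at Month 24.

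**Step 5: time between scans.** This factor is also in the model. The itemised definition and the replacement values in SAP Section 9 (MRI specific covariates) begin at Month 1. Two readings are possible:

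- Month 0 has no value and its rows drop out. The singularity disappears, but so does the Month 0 LS mean that the table lists.
- The general formula (this scan minus the previous one) supplies the Screening-to-Baseline interval. The singularity returns.

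On the second reading, under compound symmetry with complete data (200 simulated trials), visit means shift by at most about 0.23 with Month 0 and 0.11 without, if the Baseline count is unrelated to the interval. If the count falls with the interval (assumed factor 1.3 at 28 days to 0.7 at 97 days), the shifts run from −1.9 to +3.1 with Month 0 and are at most 0.02 without.

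**The case against.** The case on the other side has four parts.

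- **Scope.** The analysis is tertiary, and protocol 8.5.1 makes everything except the primary analysis exploratory. The by-Visit model for change in CUA (14.3.1) starts at Month 1 and is sound. Descriptive statistics by Visit or Period are planned anyway (SAP Section 14). A failed fit would probably be noticed in programming. All of this stands, and it limits the importance of the point.
- **Fallback.** A reader might infer that any fallback biases the visit means. The documents do not support that. Under compound symmetry with complete data and no time covariate there is no bias, and with completely random dropout it is negligible. Bias needs missingness related to Baseline, or a Baseline count related to the screening interval. Routes to the former exist: subjects who start another DMD after relapse leave trial assessments (protocol 5.5.1), and efficacy data after a delayed second course are set to missing (SAP Section 9). But subjects who merely stop the drug stay in follow-up, and nothing in the documents shows how far missingness tracks Baseline.
- **Attribution.** Removing Month 0 does not cure everything. About half of the simulated bias remains (0.65/1.22 = 53%; 1.33/2.85 = 47%), owing to the common slope and homogeneous compound symmetry. Most of the standard-error misfit remains too. This stands.
- **Literal reading.** Month 0 rows may drop out for want of a time-between-scans value. That avoids the singularity but does not deliver the specified output, so the text still needs correction.

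**Conclusion.** The point holds as a specification error in one tertiary analysis. As written, the unstructured model has no valid fit. That conclusion rests only on the SAP's definitions and the algebra, not on assumed lesion counts or dropout. A fallback with its own Month 0 variance fails likewise. A homogeneous fallback can be fitted, with the Baseline slope pulled towards 1 (0.256 against 0.163 in the complete-data simulation) and the Month 0 variance pooled into all standard errors.

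Bias in the visit means is conditional, and its size cannot be determined from the documents. The simulated values illustrate direction only, under assumed means and dropout. The primary Wilcoxon tests and the by-Visit change models in 14.3.1, 14.3.3 and 14.3.7, none of which has a Month 0 row, are not affected. The correction should still be made because it costs almost nothing.

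**What to change.** Preferred: in the 14.3.2 table, start the response at Month 1 (i = 1, 2, 3, 6, 12, 15, 18, 24), keep the Baseline score as covariate and show the Baseline value descriptively beside the LS means. This matches the by-Visit change model in 14.3.1, removes the singularity and needs no new time-between-scans value.

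Alternative: keep Month 0 in the response, drop the Baseline score from the adjusting factors, and add a Screening-to-Baseline line to the time-between-scans definition in Section 9. Without that line the Month 0 rows still lack a covariate.

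The cost is one edited table cell and one line of code for the first option, or one deleted factor and one added definition for the second. No new data or scan readings are needed.
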